#### 4.4. Safety Review Meeting Committee

Safety Review Meetings (SRMs) will be held to review blinded safety data (such as AEs, vital signs, ECGs, and safety labs) and PK (if available) when 25%, 50%, and 75% of the subjects are completed. Data to be reviewed may not necessarily be validated and cleaned (data query resolution may be pending). Data will be reviewed blinded (treatment assignment will not be revealed) unless unblinding is deemed necessary for the SRM committee.

The SRM members will include the regional Lead Investigator(s) or representative, CuraSen Chief Medical Officer, CuraSen Medical Monitor(s), and Clinical Research Study Manager. Additional members may be added as needed (e.g., statistician, PK scientist). The SRM committee will monitor subject safety and recommend whether to continue with dosing, to modify the protocol, to perform additional safety assessments and/or reviews, to delay or terminate subject enrollment, or to decrease and/or increase sample size based on emerging

Sponsor: CuraSen Therapeutics, Inc.  
Protocol Number: CST103/CST107-CLIN-011  
Version and Date: [REDACTED] v1.0 / 24May2022

safety data from this study or emerging safety, PK, and pharmacodynamics data from other ongoing and completed CuraSen studies.

#### 4.5. Interim Analysis

No formal interim analysis is planned for this study. Accruing data will be evaluated informally on an ongoing basis.

#### 4.6. Timing of Analyses

The full set of analyses summarized in this SAP will be generated upon final study database lock.

### 5. DATA ANALYSIS CONSIDERATIONS

All analyses will be conducted based on SAS 9.4 or higher.

All data in the database will be presented in by-subject data listings.

Unless otherwise stated, all listings will be sorted by cohort, disease type, treatment sequence, subject number, and assessment date (and time, if available).

Unless stated otherwise, continuous data will be summarized by cohort, disease type, treatment sequence and overall based on n, mean, median, standard deviation (SD), minimum value, and maximum value.

Unless stated otherwise, categorical data will be summarized by cohort, disease type, treatment sequence and overall using n and percentage based on the number of nonmissing values.

- The number of missing values will be presented as a separate category with no percentage, but only if one or more subjects are missing data.
- Counts of zero will be presented without percentages.

#### Precision

- Mean and Median: one additional decimal place to that reported for Minimum and Maximum
- SD: two additional decimal places than the Minimum and Maximum
- Percentages: reported to one decimal place
- P-values will be reported to four decimal places. If the value is below 0.0001 it will be noted as < 0.0001; if the value above 0.9999 it will be noted as > 0.9999.

Unless otherwise noted, statistical inference will be based on a 5% significance level (i.e. 95% confidence intervals will be produced).

Sponsor: CuraSen Therapeutics, Inc.  
Protocol Number: CST103/CST107-CLIN-011  
Version and Date: [REDACTED] v1.0 / 24May2022

All data up to the time of study completion/withdrawal from the study will be included in the analysis, regardless of duration of treatment.

Numbering for data displays will be based on ICH E3.

### 5.1. Stratification and Covariates

There are no formal plans for analysis stratification.

### 5.2. Evaluation of Subgroups

There are no formal plans for examining subgroups.

### 5.3. Multiple Comparisons and Multiplicity

This study is descriptive in nature and informal testing of multiple endpoints may be performed. Given the exploratory nature of the comparisons, no adjustment of Type I error is planned.

## 6. GENERAL DATA HANDLING CONVENTIONS

### 6.1. Reference Dates

- Screening date is defined as the eCRF provided date on which a subject was screened for trial entry.
- Treatment start date is defined as the date of first dose of study drug. Each treatment period will have a treatment start date (i.e., in order to determine AEs occurring during a treatment).
- Treatment end date is defined as the date of last dose of study drug.
- Safety data, such as AEs and laboratory assessments will use the treatment start date as a reference date.
- Study day will be based on treatment start date as a reference date.

### 6.2. Study Day and Duration Variables

Study day or duration calculations will generally be defined as the following, assuming non-missing dates:

- date of interest – reference date + 1, when the date of interest  $\geq$  reference date;
- otherwise, date of interest – reference date.

If either date is missing, reference day or duration calculations will not be performed. Date imputation will be performed as identified in Section 6.4.

Sponsor: CuraSen Therapeutics, Inc.  
Protocol Number: CST103/CST107-CLIN-011  
Version and Date: █████ v1.0 / 24May2022

In general, study day will be based on the treatment start date as the reference. As such, study day would either have a negative value if collected before dosing or a positive value if collected on or after the day of drug dosing; there will be no study day zero.

Duration of time is dependent on reference dates and will be calculated in a manner similar to that of the reference date calculation, assuming that dates of interest will strictly follow reference dates (e.g., no negative values). For example, duration of time in study is defined as the end of study date – informed consent date + 1. Duration of treatment is defined as treatment end date – treatment start date + 1, where treatment end date is the date of last dose of study drug.

### 6.3. Baseline and Post-Baseline Changes

Unless stated otherwise, baseline and post-baseline change values will be based on the following:

- Baseline will be based on the last non-missing value collected prior to or on the treatment start date and time. Post-baseline values will be those collected after the treatment start date and time.
- Change from baseline is defined as: value – baseline value.

### 6.4. Missing Data and Data Imputation Rules

All attempts will be made by the Data Management team to ensure completeness of data. Generally, missing data will not be imputed, and will be presented as collected in the study database.

In cases where adverse event (AE) or medication dates are missing, the imputation methods described in Appendix 1 will be used to determine flags for treatment-emergent events, and concomitant medications.

Other missing data methods will be proposed within the respective analysis section, as needed.

### 6.5. Multiple Assessments and Visit Windows

Nominal visits (e.g. those identified by the study CRF) will be the basis of summarization and statistical analysis; no visit date windowing will be conducted. Unscheduled data may be included in summaries of specific abnormalities any time post-baseline and subject data listings.

## 7. STUDY SUBJECT DATA

### 7.1. Analysis Populations

**Intent to Treat Set (ITT):** All subjects who have signed informed consent and have been randomized to a treatment sequence. Subjects will be analyzed according to the treatment sequence assigned at randomization. The ITT will be the analysis set for disposition and select baseline characteristic analyses.

Sponsor: CuraSen Therapeutics, Inc.  
Protocol Number: CST103/CST107-CLIN-011  
Version and Date: [REDACTED] v1.0 / 24May2022

**Safety Set (SAF):** All subjects who received at least 1 dose of study drug (CST-103/CST-107 or placebo). Subjects will be reported based on the treatment and dose received. The Safety Set will be used for the reporting of safety analyses.

**Full Analysis Set (FAS):** All randomized subjects who have taken at least 1 dose of blinded study drug (CST-103/CST-107 or Placebo). Subjects will be analyzed according to the treatment assigned at randomization. The Full Analysis Set will be used for evaluating the pharmacodynamic endpoints, and selected secondary endpoints.

**Per-Protocol Set (PPS):** A subset of the Full Analysis Set who sufficiently complied with the protocol. The analysis set will only include subjects without protocol deviations classified as “major”. The Per Protocol Set may be used for selected safety analyses.

**BioStamp Set (BSS):** A subset of the Full Analysis Set who have at least one BioStamp measurement during the baseline period each of the post-baseline periods. The BioStamp Set will be used for demographics and the BioStamp related endpoints.

**Pharmacokinetic Set (PKS):** All subjects in the Safety Set who have at least one valid plasma concentration assessment for CST-103 or CST-107. Subjects will be analyzed according to the treatment received. The PKS will be the analysis set for PK concentration and PK parameter analyses.

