#### *Activity Tracking (AUS/NZ Subjects Only)*

The BioStamp nPoint device will be worn continuously for the 7 days prior to the Treatment Period 1 through the Day 1 visit (Baseline period), and re-dispensed at each of the Day 1 Visits in both periods, worn for 14 days, and removed on Day 14. During each of the three periods in which the subject wears the device, the device calculates 49 cumulative metrics for each day worn within the period. The metrics are then aggregated by study period (Baseline period, Treatment Period 1, Treatment Period 2). The 7 metrics related to activity tracking/classification are:

- Percent Wake Time defined as the percentage of sensor wear time spent awake. All time not spent awake is time spent asleep (identified in the raw data as `wake_percent`).
- Percent Moving Time defined as the percentage of waking time spent moving (sum of walking and other) (identified in the raw data as `moving_percent`).
- Percent Moving Other Time defined as the percentage of time spent moving but not walking (identified in the raw data as `moving_other_percent`).
- Percent Walking Time defined as the percentage of time spent walking

Sponsor: CuraSen Therapeutics, Inc.  
Protocol Number: CST103/CST107-CLIN-011  
Version and Date: [REDACTED] v1.0 / 24May2022

- Moving Activity Count defined as the activity counts per hour during moving periods (identified in the raw data as activity\_moving).
- Resting Activity Count defined as the activity counts per hour during resting periods
- Wake Activity Count defined as the activity counts per hour during moving and resting periods (identified in the raw data as activity\_resting).

All BioStamp aggregated data will be listed.

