### *BioStamp (AUS/NZ Subjects Only)*

In addition to activity tracking/classification, the BioStamp nPoint device will continuously track posture (classifications, durations, and temporal patterns), sleeping patterns (duration, posture, transitions, and activity counts), autonomic function (heart rate variability (HRV)), and temporal pedometry via daily step count and gait cadence. There are 29 daily metrics calculated by the BioStamp device related to posture, sleeping patterns, autonomic function, and temporal pedometry. These metrics are then aggregated by study period (Baseline period, Treatment Period 1, Treatment Period 2).

- Posture:
  - Percent Resting Time defined as the percentage of waking time spent resting (sum of lying, sitting, and standing) (identified in the raw data as resting\_percent).
  - Percent Lying Time defined as the percentage of waking time spent lying (identified in the raw data as resting\_lying\_percent).
  - Percent Sitting Time defined as the percentage of waking time spent sitting (identified in the raw data as resting\_sitting\_percent).
  - Percent Standing Time defined as the percentage of waking time spent standing (identified in the raw data as resting\_standing\_percent).

- Percent Upright Posture defined as the percentage of resting time when the patient's posture was classified as upright. All time not classified as upright is classified as leaning (identified in the raw data as upright\_posture\_percent).
- Sleeping patterns:
  - Average Sleep Duration as defined by average hours of sleep for days that include sleep periods (identified in the raw data as avg\_sleep\_duration).
  - Average Sleep Posture Transitions as defined by the average number of sleeping posture transitions that occur per hour during sleep (identified in the raw data as sleeping\_posture\_transitions\_rate).
  - Sleeping Activity Counts as defined by activity counts per hour during sleeping periods (identified in the raw data as activity\_sleeping).
- Autonomic function:

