Heart Rate Variability (HRV) is computed for each activity period using two methods, LF/HF which is a ratio of low frequency to high frequency and RMSSD which is the root mean square of the successive differences. For each of the 8 metrics below, a set of descriptive statistics is computed (coefficient of variation, minimum, maximum, mean, 5th, 25th, 75th, 95th percentiles, standard deviation), and the mean of each parameter will be assessed using the mixed modeling described later on:

  - Sleeping HRV LF\_HF (identified in the raw data as hrv\_lfhf\_sleeping).
  - Sleeping HRV RMSSD (identified in the raw data as hrv\_rmssd\_sleeping).
  - Resting HRV LF\_HF (identified in the raw data as hrv\_lfhf\_resting).
  - Resting HRV RMSSD (identified in the raw data as hrv\_rmssd\_resting).
  - Moving HRV LF\_HF (identified in the raw data as hrv\_lfhf\_moving).
  - Moving HRV RMSSD (identified in the raw data as hrv\_rmssd\_moving).
  - Waking HRV LF\_HF (identified in the raw data as hrv\_lfhf\_wake).
  - Walking HRV RMSSD (identified in the raw data as hrv\_rmssd\_wake).
- Temporal pedometry:
  - Average Gait Cadence as defined as steps per minute during walking (identified in the raw data as avg\_gate\_cadence).
  - Step Count Rate as defined as step counts per hour during periods classified as walking (identified in the raw data as step\_count\_rate).

If a subject has at least 5 days of sensor wear within each period, the metrics will be aggregated for each period to obtain a single value. Descriptive statistics of the 17 metrics noted above, as well as the 7 activity metrics noted in Section 8.1 above, and change from baseline will be reported for both Cohort A and Cohort B subjects. A mixed model with change from baseline period as the dependent variable, baseline period value as a covariate, treatment sequence, post-baseline period (i.e., 1, 2), disease type, and treatment as fixed effects, and subject as a random effect will be analyzed for these posture, sleep, autonomic function, activity tracking, and temporal pedometry parameters for all subjects and LS means, LS mean differences, and p-values will be presented.

*Epworth Sleepiness Scale (ESS)*

Sponsor: CuraSen Therapeutics, Inc.  
Protocol Number: CST103/CST107-CLIN-011  
Version and Date: █████ v1.0 / 24May2022

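### The BioStamp treatment comparison drops subjects who lack a valid lead-in value, although for complete treatment pairs that single baseline cancels from the active-placebo contrast

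*SAP*

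**What the plan says.** SAP 8.1 (Activity Tracking) schedules one baseline, the 7 days of wear leading up to Day 1 of Treatment Period 1. The device is then "re-dispensed at each of the Day 1 Visits in both periods, worn for 14 days, and removed on Day 14". No wear is scheduled in the washout, so both treatment periods share the lead-in baseline.

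Three rules then decide who enters the treatment comparison:

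- **The set (SAP 7.1).** The BioStamp Set is "A subset of the Full Analysis Set who have at least one BioStamp measurement during the baseline period each of the post-baseline periods"; a word such as 'and' is missing before 'each'. Its use is stated: "The BioStamp Set will be used for demographics and the BioStamp related endpoints".
- **The wear rule (SAP 8.2, BioStamp).** "If a subject has at least 5 days of sensor wear within each period, the metrics will be aggregated for each period". The same section names the lead-in as one of the three periods: "These metrics are then aggregated by study period (Baseline period, Treatment Period 1, Treatment Period 2").
- **The model (SAP 8.2, BioStamp).** "A mixed model with change from baseline period as the dependent variable, baseline period value as a covariate, treatment sequence, post-baseline period", disease type and treatment as fixed effects, and subject as a random effect. LS means, their difference and p-values are reported.

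SAP 6.4 says that missing data are generally not imputed. No BioStamp model without baseline is offered. SAP 2.1 confines BioStamp data to Australia and New Zealand and gives no count of those subjects.

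**The concern.** A subject with 4 lead-in days and full wear in both treatment periods has everything needed to compare active with placebo, yet has no valid baseline, hence no change score, and is lost to the model. In a crossover the treatment effect is estimated within subject. A baseline measured once and shared by both periods is constant within subject and cannot inform that comparison.

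What is at stake is precision in a regional subset of a study of about 40 subjects. The lead-in is also the tightest of the three wear requirements: 5 of 7 days, against 5 of 14 in each treatment period.

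A second mismatch follows from the same text. Entry to the BioStamp Set needs one measurement per period, while the analysis needs 5 days. Demographics on the BioStamp Set (SAP 7.4) can therefore describe a different group from the one modelled.

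**Working it through.** **1. Who is excluded, and by which rule.** A subject with 1 to 4 lead-in days satisfies SAP 7.1 and is inside the BioStamp Set. The exclusion comes from the 5-day rule and the change-from-baseline outcome in SAP 8.2. SAP 7.1 alone removes only subjects with no lead-in measurement at all. If the 5-day rule is read period by period instead of as a condition on all three periods, a subject without a valid lead-in value still has no outcome.

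**2. Cancellation.** Let B be the lead-in value and Y the period value. For a subject with both treatment periods:

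(Y_active − B) − (Y_placebo − B) = Y_active − Y_placebo.

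The baseline covariate, sequence and disease type are also constant within subject, so with complete pairs they do not enter the treatment estimate. This was checked by REML on four simulated trials of 20 complete pairs. The SAP model, the change model without the covariate, the raw-value model and the closed-form crossover estimate agreed to five decimals in every trial (for example, 0.35512 with standard error 0.20254 from all four). Equality of the standard errors requires a subject-variance estimate above zero. The cancellation also requires no baseline-by-treatment term, and the SAP has none.

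**3. The plan's own power figure.** SAP 4.3 states at least 80% power for 0.79 SD with 20 subjects (two-sided 5%, correlation 0.3). It is stated for primary and cognition endpoints, not for BioStamp.

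- SD of the paired difference = SD × √(2 × (1 − 0.3)) = 1.183 SD.
- Noncentrality = 0.79 × √20 / 1.183 = 2.99 on 18 df, giving power of 80.6%.
- For 40 subjects and 0.54 SD, the noncentrality is 2.89 on 38 df, giving 80.3%.

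Both stated figures are reproduced.

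**4. Cost of losing complete pairs.** The documents give no lead-in failure rate, so the lost fraction f is an assumption. Standard error inflation = 1/√(1 − f) − 1:

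| f (assumed) | Rise in SE |
|---|---|
| 3% | 1.5% |
| 10% | 5.4% |
| 20% | 11.8% |
| 25% | 15.5% |

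Dropping 4 of 20 pairs in 2,000 simulated trials raised the mean standard error from 0.199 to 0.222, or 11%. On the SAP 4.3 assumptions, used only as a yardstick, power at 0.79 SD falls from 80.6% with 20 pairs to 75.8% with 18 and 70.0% with 16.

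**5. Which requirement would bind.** Assume independent daily wear with probability p:

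| p (assumed) | At least 5 of 7 lead-in days | At least 5 of 14 days in both treatment periods |
|---|---|---|
| 0.7 | 64.7% | 99.7% |
| 0.8 | 85.2% | about 100% |
| 0.9 | 97.4% | about 100% |

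Under this assumption nearly all exclusions come from the lead-in. With good wear the loss is small: at p = 0.9, f = 2.6% and the standard error rises by 1.3%.

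**The case against.** The lead-in value is not useless. The descriptive change-from-baseline summaries and the LS means of change need it, and the protocol synopsis says that the Lead-In Period is meant to establish a baseline activity profile. One common set also keeps descriptive and model outputs on the same subjects. This stands, and it limits the point to the active-placebo LS mean difference and its p-value.

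The modelled BioStamp results are secondary. SAP 8 and 8.2 call all inferential analyses exploratory, and SAP 8.1 has activity tracking, as a Cohort B primary endpoint, listed only. This also stands, and it keeps the point modest.

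A reader might go further and infer that selecting subjects on device tolerance biases the treatment comparison. The documents do not support that. Lead-in wear is recorded before any dosing, so excluding on it cannot bias the within-subject contrast; at most it narrows the group to which the result applies. Wear during treatment, which the drug could affect, would still be a condition under the remedy.

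A reader might also infer that a substantial share of pairs will be lost. Nothing in the documents says so; with good wear the loss is close to nil.

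**Conclusion.** The point holds in a limited form. SAP 8.2, together with the BioStamp Set in SAP 7.1, makes a valid lead-in value a condition for entering the BioStamp treatment comparison. For subjects with both treatment periods that value contributes nothing to the contrast. The result is a possible loss of precision, without bias, across the modelled BioStamp metrics (24 by the SAP's count of 17 plus 7; the bullets list 18 plus 7).

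The size is unknown, because the documents give neither lead-in compliance nor the number of Australian and New Zealand subjects. Over assumed losses of 3% to 25% of complete pairs, the standard error rises by about 1.5% to 15%. Cancellation is exact for complete pairs only. The difference between the one-measurement and 5-day thresholds is a separate inconsistency in the text and depends on none of these assumptions.

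**What to change.** In SAP 8.2, for the active-placebo contrast, include Full Analysis Set subjects with at least 5 wear days in both treatment periods, whatever their lead-in wear. Fit the mixed model to the period values, with sequence, period, disease type and treatment as fixed effects and subject as a random effect. Everyone who meets the 5-day rule in all three periods remains in, so the change can only keep or add complete pairs. Do not extend this baseline-free analysis to subjects with only one valid treatment period: cancellation fails for them, and a baseline covariate can help there.

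Keep the lead-in requirement for the change-from-baseline summaries and for the planned baseline-adjusted model, retained as supportive.

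In SAP 7.1, restore the missing word and align the set's wear threshold with the 5-day rule, so that its demographics describe the subjects analysed.

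The cost is a few lines of SAP wording before database lock, with no new data. Protocol 8.7 asks for baseline values in the model only as appropriate, and Protocol 8.2 lets the SAP define further populations, so the change stays within the protocol.

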## 7.2. Subject Disposition

Subject disposition will be summarized using the ITT set. Summaries will include the number and percent of subjects: screened, enrolled, in each analysis population, completing the study, and discontinuing study prematurely, including a description of the reason for early withdrawal. Reasons for withdrawal will include the following:

- Adverse Event
- Lost to follow-up
- Subject withdrew consent
- Protocol violation/non-compliance
- Investigator decision
- Study terminated by sponsor
- Pregnancy
- Study burden
- Tested positive for COVID-19
- Fear of contracting COVID-19
- Other

Data will be presented by study cohort, disease criteria, and sequence.

Screen failures, analysis populations, and final subject disposition status will be listed. Visit dates and reasons for visits not done will also be listed.

Sponsor: CuraSen Therapeutics, Inc.  
Protocol Number: CST103/CST107-CLIN-011  
Version and Date: [REDACTED] v1.0 / 24May2022

